## **Appendix 5 Declaration of Helsinki**

### Recommendations Guiding Medical Doctors in Biomedical Research Involving Human Subjects

#### I. BASIC PRINCIPLES

1. Biomedical research involving human subjects must conform to generally accepted scientific principles and should be based on adequately performed laboratory and animal experimentation and on a thorough knowledge of the scientific literature.
2. The design and performance of each experimental procedure involving human subjects should be clearly formulated in an experimental protocol which should be transmitted to a specially appointed independent committee for consideration, comment and guidance.
3. Biomedical research involving human subjects should be conducted only by scientifically qualified persons and under the supervision of a clinically competent medical person. The responsibility for the human subject must always rest with a medically qualified person and never rest with the subject of the research, even though the subject has given his or her consent.
4. Biomedical research involving human subjects cannot legitimately be carried out unless the importance of the objective is in proportion to the inherent risk to the subject.
5. Every biomedical research project involving human subjects should be preceded by careful assessment of predictable risks in comparison with foreseeable benefits to the subject or to others. Concern for the interests of the subject must always prevail over the interests of science and society.
6. The right of the research subject to safeguard his or her integrity must always be respected. Every precaution should be taken to respect the privacy of the subject and to minimize the impact of the study on the subject's physical and mental integrity and on the personality of the subject.
7. Doctors should abstain from engaging in research projects involving human subjects unless they are satisfied that the hazards involved are believed to be predictable. Doctors should cease any investigation if the hazards are found to outweigh the potential benefits.
8. In publication of the results of his or her research, the doctor is obliged to preserve the accuracy of the results. Reports of experimentation not in accordance with the principles laid down in this Declaration should not be accepted for publication.
9. In any research on human beings, each potential subject must be adequately informed of the aims, methods, anticipated benefits and potential hazards of the study and the discomfort it may entail. He or she should be informed that he or she is at liberty to abstain from participation in the study and that he or she is free to withdraw his or her

consent to participation at any time. The doctor should then obtain the subject's given informed consent, preferably in writing.

10. When obtaining informed consent for the research project the doctor should be particularly cautious if the subject is in a dependent relationship to him or her or may consent under duress. In that case, the informed consent should be obtained by a doctor who is not engaged in the investigation and who is completely independent of this official relationship.
11. In case of legal incompetence, informed consent should be obtained from the legal guardian in accordance with national legislation. Where physical or mental incapacity makes it impossible to obtain informed consent, or when the subject is a minor, permission from the responsible relative replaces that of the subject in accordance with national legislation.
12. The research protocol should always contain a statement of the ethical considerations involved and should indicate that the principles enunciated in the present Declaration are complied with.

## II. MEDICAL RESEARCH COMBINED WITH PROFESSIONAL CARE (CLINICAL RESEARCH)

13. In the treatment of the sick person, the doctor must be free to use a new diagnostic and therapeutic measure, if in his or her judgment it offers hope of saving life, reestablishing health or alleviating suffering.
14. The potential benefits, hazards and discomforts of a new method should be weighed against the advantages of the best current diagnostic and therapeutic methods.
15. In any medical study, all subjects - including those of a control group, if any, should be assured of the best proven diagnostic and therapeutic methods.
16. The refusal of the subject to participate in a study must never interfere with the doctor subject relationship.
17. If the doctor considers it essential not to obtain informed consent, the specific reasons for this proposal should be stated in the experimental protocol for transmission to the independent committee.
18. The doctor can combine medical research with professional care, the objective being the acquisition of new medical knowledge, only to the extent that medical research is justified by its potential diagnostic or therapeutic value for the subject.

### III. NON-THERAPEUTIC BIOMEDICAL RESEARCH INVOLVING HUMAN SUBJECT (NONCLINICAL BIOMEDICAL RESEARCH)

19. In the purely scientific application of medical research carried out on a human being, it is the duty of the doctor to remain the protector of the life and health of that person on whom biomedical research is being carried out.
20. The subjects should be volunteers - either healthy person or subjects for whom the experimental design is not related to the subject's illness.
21. The Investigator or the team should discontinue the research if in his/her or their judgment it may, if continued, be harmful to the individual.
22. In research on man, the interest of science and society should never take precedence over consideration related to the well-being of the subject.

20.	Tables	19
21.	Listings	21
22.	Figures	21

List of Abbreviations

AE	Adverse Event
AHD	Aqueous Humor Dynamics
CI	Confidence Interval
CS	Clinically Significant
CSR	Clinical Study Reports
eCRF	Electronic Case Report Form
ETDRS	Early Treatment of Diabetic Retinopathy Study
EVP	Episcleral Venous Pressure
HR	Heart Rate
ICH	International Conference on Harmonization
IOP	Intraocular Pressure
IRB	Institutional Review Board
IP	Investigational Product
logMAR	Logarithm of the Minimum Angle of Resolution
MedDRA	Medical Dictionary for Regulatory Activities
mITT	Modified Intent-to-Treat
mmHg	Millimeters Mercury
NCS	Not Clinically Significant
OHT	Ocular Hypertension
PDF	Portable Document Format
POAG	Primary Open-Angle Glaucoma
PP	Per Protocol
PT	Preferred Term
RTF	Rich Text Format
SAE	Serious Adverse Event
SAP	Statistical Analysis Plan
SOC	System Organ Class
TEAE	Treatment-Emergent Adverse Event
VA	Visual Acuity
WHO	World Health Organization

1. Introduction

The purpose of this statistical analysis plan (SAP) is to describe the planned analyses and reporting for protocol AR-13324-CS206, version Amendment 1 dated 16Aug2017.

This SAP is being written with due consideration of the recommendations outlined in the most recent International Conference on Harmonization (ICH) E9 Guideline entitled Guidance for Industry: Statistical Principles for Clinical Trials and the most recent ICH E3 Guideline, entitled Guidance for Industry: Structure and Content of Clinical Study Reports (CSR).

This SAP describes the data that will be analyzed and the subject characteristics, efficacy, and safety assessments that will be evaluated. This SAP provides details of the specific statistical methods that will be used. The statistical analysis methods presented in this document will supersede the statistical analysis methods described in the clinical protocol. If additional analyses are required to supplement the planned analyses described in this SAP they may be completed and will be identified in the CSR.

2. Study Objectives

The primary objective of this study is to evaluate the effect on trabecular outflow facility of Netarsudil Ophthalmic Solution 0.02%, compared to Placebo, in subjects with primary open-angle glaucoma (POAG) or ocular hypertension (OHT).

The secondary objectives are: (i) to evaluate the effect on intraocular pressure (IOP) and episcleral venous pressure (EVP) of Netarsudil Ophthalmic Solution 0.02% compared to Placebo in subjects with POAG or OHT; (ii) to evaluate the ocular and systemic safety of Netarsudil Ophthalmic Solution 0.02%.

2.1 Primary Variables

The primary efficacy variable for the study is trabecular (tonographic) outflow facility.

2.2 Secondary Variables

The secondary efficacy variables include the following:

- IOP
- EVP

2.3 Safety Variables

The assessment of safety will be evaluated by:

- Ocular signs and symptoms /Adverse Events (AE)
- Visual Acuity (VA)
- Biomicroscopy of anterior segment including evaluation of cornea, conjunctiva, and anterior chamber

- Ophthalmoscopy
- Pachymetry and Gonioscopy (screening only)
- Heart rate (HR) and blood pressure

2.4 Statistical Hypotheses

The primary endpoint is the mean change from baseline in the mean diurnal trabecular outflow facility on Day 8. The null and alternative hypotheses, based on the primary variable are as follows:

H01: The difference between study eyes treated with Netarsudil Ophthalmic Solution 0.02% and study eyes treated with Placebo, in the mean change from baseline of mean diurnal trabecular outflow facility = 0 on Day 8.

H11: The difference between study eyes treated with Netarsudil Ophthalmic Solution 0.02% and study eyes treated with Placebo, in the mean change from baseline of mean diurnal trabecular outflow facility > 0 on Day 8.

3. Study Design and Procedures

3.1 General Study Design

This will be a double-masked, Placebo-controlled, paired-comparison study conducted at approximately 2 centers in the US to evaluate the effect of treatment with Netarsudil Ophthalmic Solution 0.02% (Netarsudil) on trabecular outflow facility. Netarsudil will be administered to one eye and Placebo to the contralateral eye once daily, 1 drop in the morning (QD, AM), in adult subjects at least 18 years of age with POAG or OHT. Study medication will be administered for 7 consecutive days, although the total time of subject participation in the study (including washout from prior treatment, if necessary) may be up to 7 weeks.

Subjects will be eligible to enroll in the study if they have a current diagnosis of POAG or OHT in both eyes (POAG in one eye and OHT in the contralateral eye is also acceptable), and may be treatment-naïve or taking topical ocular hypotensive medication. If necessary, subjects who agree to participate in the study will be required to washout from their current IOP-lowering treatment for a minimum specified period of time (5 days to at least 4 weeks), according to the type of treatment. Subjects will attend a total of 3 study visits: a screening visit (Visit 1), to be conducted up to 6 weeks prior to a qualification visit (Visit 2, Day 1, baseline), and a final visit after 7 days on-treatment (Visit 3, Day 8, exit) where a member of the site staff will administer their 7th dose after completing their 08:00 hour assessments.

Both eyes must qualify for the study with an unmedicated (post-washout or treatment-naïve) IOP of >20 mmHg but <30 mmHg at 08:00 hours and >17 mmHg but <30 mmHg at 13:00 and 16:00 hours at the qualification visit. In order to be randomized into the study, eligible subjects must meet all of the

inclusion, and none of the exclusion criteria at both the screening and at the qualification visit, following washout from their current ocular hypotensive treatment, if required.

If the subject continues to be eligible, they will be randomized at the end of their qualification visit (Visit 2, Day 1, baseline) to receive Netarsudil Ophthalmic Solution 0.02% in one eye and Placebo in the contralateral eye for 7 days, QD (AM). Subjects will be asked to begin self-administration of their assigned medications in the morning on Day 2 following their baseline (Day 1) visit. Subjects will be instructed to administer 1 drop from each bottle of their study medication into the assigned eye for that bottle, every morning at approximately the same time (between 08:00 and 10:00 hours) for 6 consecutive days. On the day of the final (exit) visit (Visit 3, Day 8), subjects will return to the site at 08:00 hours for their final dose of study medication and to complete their on-treatment measurements before exiting.

Safety measures (including VA, biomicroscopy, and AEs) will be evaluated at all visits. Efficacy assessments will include IOP at 08:00, 13:00 and 16:00 hours, and trabecular outflow facility and EVP, which will be measured at 13:00 and 16:00 hours. Trabecular outflow facility (primary endpoint) and IOP (secondary endpoint) will be collected in all subjects. The other secondary endpoint, EVP, will be measured in a subset of subjects.

3.2 Schedule of Visits and Assessments

The schedule of visits and assessments is provided below.

Day (D)/Week(W)/Month(M)	Screening	Quali	fication/	Day 1	E	xit/Day	8
Visit	1	2	2/Baseline ⁷		3/On-drug ⁷		\mathbf{g}^7
Hour		08:00	13:00	16:00	08:00	13:00	16:00
Informed Consent	X						
Inclusion/Exclusion	X	X	X	X			
Demography	X						
Medical/Ophthalmic History	X						
HR/BP	X	X			X		
Pregnancy test ¹	X						
Ocular symptoms/AEs ²	X	X			X		
VA (ETDRS)	X	X			X		
IOP	X	X	X	X	X	X	X
Biomicroscopy	X	X			X		
Gonioscopy ³	X						
Pachymetry ³	X						
Ophthalmoscopy (dilated)	X						

Eye-Drop Instillation Evaluation	X					
EVP ⁴	X^6	X	X		X	X
Tonography		X	X		X	X
Study meds dispensed			X			
Study meds instilled ⁵				X		
Study meds collected				X		
Study completed						X

- 1. Pregnancy test for females of child-bearing potential only.
- 2. Ocular Symptoms: Patients will be queried at each visit "how are your eyes feeling" and TEAEs will be documented on the AE form. Additional symptoms reported after screening and before randomization will be documented on the medical history form.
- 3. Gonioscopy within 3 months prior to screening, and Pachymetry within 1 week of screening are acceptable.
- 4. Measurement of EVP will only be conducted at 1 site
- 5. Study medications to be instilled after 08:00 hour measurements are completed on Day 8.
- 6. Only an assessment of a suitable episcleral vein prior to performing EVP measurements at Visit 2/Day 1. If unable to assess at screening, it may be assessed at Visit 2 during the 08:00 timepoint
- 7. A visit variation of \pm 30 minutes is allowed.

4. Study Treatments

4.1 Method of Assigning Subjects to Treatment Groups

Enrolled subjects will receive both investigational products (IPs), Netarsudil Ophthalmic Solution 0.02% (QD AM) and Placebo (QD AM). Individual eyes will be randomized to receive active treatment or Placebo; one treatment will be dosed in the right eye (OD), and the other treatment will be dosed in the left eye (OS). Each IP dose will be self-administered by the study subjects. For subjects deemed unable to self-administer the doses at the qualification visit (Visit 2, Day 1), a guardian or caregiver will be asked to administer the medication.

Masked kits containing identical bottles of IP labelled "right eye" or "left eye" will be provided to all subjects at the end of Visit 2 (Day 1, qualification, baseline). They will be instructed to begin self-administration in the morning of Day 2 at approximately the same time each day (between 08:00 and 10:00 hours) for the following 6 days, returning to the site on Day 8 where study personnel will administer the final dose.

A randomization schedule will be prepared by an independent individual (unmasked personnel) who is not involved in the day-to-day conduct of the study. Randomization will be stratified by site using permuted blocks, such that there will be an approximately equal number of subjects assigned to each of the two sequences ([Active Left Eye and Placebo Right Eye] and [Active Right Eye and Placebo Left Eye]) at each site.

The randomization schedule will be provided to the investigational site. The eligible subjects will be assigned a randomization number at the end of Visit 2, Day 1. Randomization numbers will be assigned sequentially to subjects in the order in which they become eligible for randomization. The site staff will dispense to the subject the study kit labeled with the corresponding randomization number. Each kit will contain one bottle of each product labeled "right eye" (OD) and "left eye" (OS). The randomization number will be recorded on the subject's source document and electronic case report form (eCRF).

5. Sample Size and Power Considerations

Among the AHD parameters, trabecular outflow facility is of key interest and therefore used for the overall sample size calculation. Assuming a one-sided alpha = 0.05, a standard deviation for the difference between treatments in the mean change from baseline in diurnal means of 0.07 mmHg (calculated with a common standard deviation of 0.06 μ L/min/mmHg within each treatment and a correlation of 40% between eyes within the same subject), and a difference in mean change from baseline between treatments (Active - Placebo) in diurnal means of 0.08 μ L/min/mmHg, a sample size of 16 subjects (32 eyes) yields greater than 95% power.

Assuming approximately 20% of the randomized subjects will be non-evaluable, i.e. either non-responders (see modified intent-to-treat [mITT] population below for the definition of responder) or discontinue prior to Day 8, the required number of subjects to be randomized will be 20 subjects.

6. Data Preparation

Study data will be recorded via eCRFs. Each authorized study staff member will receive a unique access account in order to use the Electronic Data Capture (EDC) system. Access accounts will not be shared among study staff. Authorized users will make entries and/or changes to the eCRF via a secure internet access. Each completed set of eCRFs will be reviewed by the Investigator who will then electronically sign and date the eCRF confirming that data for the subjects are complete and accurate.

All final analyses outlined in this document will be carried out after the following have occurred:

- All data management requirements are met according to standard operating procedures, including data entry, performance of edit and validation checks, documentation and resolution of data queries, and database lock with written authorization provided by appropriate

 and Sponsor personnel;
- Protocol deviations have been identified and status defined (major/minor deviations);
- Analysis populations have been determined; and
- Randomized treatment codes have been unmasked.

7.1 Modified Intent-to-Treat

The mITT population will include all randomized subjects who meet the following criteria: 1) have received at least one dose of study medication, 2) have all baseline measurements and all post-baseline measurements for trabecular outflow facility, and 3) have mean diurnal IOP that is at least 2 mmHg lower than baseline mean diurnal IOP in the same eye treated with Netarsudil (responders).

These subjects will be analyzed in accordance with the treatment they actually received, even if that treatment is different from the planned treatment (i.e., in the event of a randomization or dispensing error, subjects in the mITT population will be analyzed as treated). The mITT population will serve as the primary analysis population for efficacy variables.

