### **9.3 Analysis Populations**

#### **9.3.1 Modified Intent-to-Treat (mITT) Population**

The modified intent-to-treat (mITT) population will include all randomized subjects who meet the following criteria: 1) have received at least one dose of study medication, 2) have all baseline measurements and all post-baseline measurements for trabecular outflow facility, and 3) have mean diurnal IOP that is at least 2 mmHg lower than baseline mean diurnal IOP in the same eye treated with Netarsudil (responders).

These subjects will be analyzed in accordance with the treatment they actually received, even if that treatment is different from the planned treatment (i.e., in the event of a randomization or dispensing error, subjects in the mITT population will be analyzed as treated). The mITT population will serve as the primary analysis population for efficacy variables.

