7.2 Per Protocol

The per protocol (PP) population is a subset of the mITT, which will include those subjects who do not have major protocol violations likely to seriously affect the primary outcome of the study as judged by a masked evaluation prior to the unmasking of the study treatment. These subjects will be analyzed in accordance with the treatment they actually received, even if that treatment is different from the planned treatment. The analysis with PP population is secondary.

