12.1 Dosing Compliance

A subject listing of study drug administration (i.e., showing whether subject used study eye drops for all seven days or not) will be produced.

13. Efficacy Analyses

All efficacy analyses will be conducted using the mITT population. If mITT is different from PP population, then the analyses will be repeated for the PP population.

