13.1 Primary Analysis

The primary efficacy endpoint is the mean change from baseline in mean diurnal trabecular outflow facility (average of 13:00 and 16:00 hour measurements) per treatment on Day 8. Baseline mean diurnal outflow facility is defined as the average of 13:00 and 16:00 hour measurements on Day 1, Visit 2.

The null and alternative hypotheses, based on the primary endpoint, are as follow:

H01: The difference between study eyes treated with Netarsudil Ophthalmic Solution 0.02% and study eyes treated with Placebo, in the mean change from baseline of mean diurnal trabecular outflow facility = 0 on Day 8.

H11: The difference between study eyes treated with Netarsudil Ophthalmic Solution 0.02% and study eyes treated with Placebo, in the mean change from baseline of mean diurnal trabecular outflow facility > 0 on Day 8.

The null hypothesis will be tested using a paired t-test with alpha=0.05. One-sided p-values, two-sided 90% confidence intervals (CI), and two-sided 95% CIs will be presented. The trabecular outflow facility will be summarized by treatment and visit/time point using continuous descriptive statistics (and listed by subject.

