13.2 Secondary Analyses

The secondary efficacy endpoints include:

- Mean change from baseline in mean diurnal IOP (average of 13:00, and 16:00 hour measurements) and mean diurnal EVP (average of 13:00 and 16:00 hour measurements) per treatment on Day 8
- Mean diurnal values for all AHD (trabecular outflow facility, IOP, EVP) per treatment on Day 8
- Mean values for all AHD at the individual 13:00 and 16:00 hourtime points per treatment on Day 8
- Mean change from baseline for all AHD at the individual 13:00 and 16:00 hour time points per treatment on Day 8. Baseline individual time points are defined as the corresponding measurements on Day 1, Visit 2
- Percent (%) change from baseline in diurnal means for all AHD per treatment on Day 8
- Percent (%) change from baeline at the individual 13:00 and 16:00 time points for all AHD per treatment on Day

Mean change from baseline in mean diurnal IOP and EVP will be analyzed similarly to the primary endpoint.

Similar to the primary efficacy analysis, mean differences in diurnal means of AHD measures and mean differences at the individual time points will be tested with paired t-tests. One-sided p-values, two-sided 90% CIs, and two-sided 95% CIs will be presented. Means within each treatment comparing diurnal mean on Day 8 with baseline diurnal mean and comparing individual time points on Day 8 with the corresponding time points at baseline visit will also be tested using paired t-tests. The same inferential statistics will be presented for these.

Mean percent change from baseline in diurnal means of AHD measures and mean percent change from baseline in AHD measures at individual timepoints will be tested using paired t-tests. The same inferential statistics will be presented for these.

All secondary efficacy endpoints will be summarized by treatment and visit/time point using continuous descriptive statistics.

14. Exploratory Analyses

Not applicable.

15. Safety Analyses

All safety analyses will be conducted using the Safety population.

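### The primary efficacy population keeps only subjects whose netarsudil eye fell by at least 2 mmHg, so every planned efficacy test is filtered on an outcome

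*SAP*

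**What the plan says.** SAP 7.1 sets three conditions for the mITT population: at least one dose, complete facility data, and a third under which subjects must "have mean diurnal IOP that is at least 2 mmHg lower than baseline mean diurnal IOP in the same eye treated with Netarsudil (responders". The Protocol synopsis and Protocol 9.3.1 carry the same rule, and 9.3.1 adds: "The mITT population will serve as the primary analysis population for efficacy variables".

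No efficacy analysis is planned outside that set. SAP 13 states: "All efficacy analyses will be conducted using the mITT population". The only repeat is in the per-protocol population, and SAP 7.2 says "The per protocol (PP) population is a subset of the mITT". SAP 14 plans no exploratory analyses, and the safety population serves safety only.

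The primary endpoint is facility (SAP 13.1): "The primary efficacy endpoint is the mean change from baseline in mean diurnal trabecular outflow facility (average of 13:00 and 16:00 hour measurements". Diurnal IOP is averaged over the same two hours (SAP 8.3), and its change is a secondary endpoint tested two ways in SAP 13.2. Between eyes: "Mean change from baseline in mean diurnal IOP and EVP will be analyzed similarly to the primary endpoint". Within each treatment: "Means within each treatment comparing diurnal mean on Day 8 with baseline diurnal mean".

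The restriction is deliberate and enters the sample size (SAP 5): "Assuming approximately 20% of the randomized subjects will be non-evaluable, i.e. either non-responders", or lost before Day 8.

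**The concern.** Randomising eyes protects the paired comparison only while pairs are kept or dropped without regard to outcome. Criterion 3 drops pairs according to Day 8 IOP in the netarsudil eye; the placebo eye faces no such condition. Three things follow.

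- The filter variable is also a tested endpoint. Its within-netarsudil test is settled by the admission rule, and its between-eye test is pushed towards netarsudil.
- The primary facility test is pushed the same way if a larger IOP fall goes with a larger facility rise in the same eye. The IOP equation in Protocol 1.1 points in that direction, and Protocol 3.2 regards facility as the likely main mechanism.
- The objective concerns subjects with POAG or OHT, whereas the estimate would describe IOP responders. No unfiltered efficacy analysis is planned against which to check it.

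**Working it through.** **1. The plan's own figure.** Inputs from SAP 5: facility-change SD 0.06, between-eye correlation 0.4, difference 0.08, one-sided 5%, n = 16.

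- SD of the difference = 0.06 × √(2 × (1 − 0.4)) = 0.0657, given in the plan as 0.07.
- Paired t-test power (noncentral t, 15 df, SD 0.07) = 99.7%, so the claim of more than 95% is reproduced.
- 16 / (1 − 0.2) = 20 randomised, also reproduced.

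**2. Within-netarsudil diurnal IOP test.** Every retained fall is at least 2 mmHg. Baseline IOP is below 30 mmHg at entry, so no fall can exceed 30. The smallest t arises when one eye falls by 30 and the rest by exactly 2:

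- mean = (28 + 2n)/n and standard error = 28/n, so t = 1 + n/14.
- n = 16: t = 2.14 against a critical value of 1.753. Rejection is certain.
- n = 12: 1.86 against 1.796, still certain. n = 10: 1.71 against 1.833, no longer strictly certain.

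In smaller mITT sets, simulated rejection with no true change is over 99% when at least 3 subjects are kept.

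**3. Between-eye IOP test.** Let μ and SD describe netarsudil-eye IOP change, ρ the between-eye correlation, z = (−2 − μ)/SD and λ = φ(z)/Φ(z). With equal SDs, a proportion Φ(z) is kept and the mean difference shifts by −(1 − ρ) × SD × λ. The documents give no SD or correlation for IOP change. I assume SD 2 to 3 mmHg and borrow ρ = 0.4 from facility.

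- No change in either eye: the shift is −0.6 × SD × φ(2/SD)/Φ(−2/SD) = −1.83 / −2.05 / −2.28 mmHg for SD 2 / 2.5 / 3.
- 80% kept: λ = φ(0.8416)/0.8 = 0.35, so the shift is −0.21 × SD = −0.42 / −0.53 / −0.63 mmHg.

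Rejection rates are from multivariate-normal simulation, 20 randomised, one-sided 5%:

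| Truth | SD (mmHg) | Mean number kept | Between-eye test rejects |
|---|---|---|---|
| No change in either eye | 2 / 2.5 / 3 | 3.2 / 4.2 / 5.0 | about 44% given at least 3 kept; 28 / 36 / 41% of all trials |
| Both eyes fall 2 mmHg | 2 / 3 | 10 / 10 | 40 / 41% |
| Both eyes fall equally, 80% kept | 2 / 3 | 16 / 16 | 19 / 19% |

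Trials with fewer than 3 kept (36 / 17 / 9% in the first row) count as non-rejections in the all-trials rates. In the third row, ρ from 0.8 down to 0 gives 11% to 27%. Without the filter the same test rejects in about 5% of trials.

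With a real effect, 80% responders and SD 2.5, the true difference is −(2 + 0.8416 × 2.5) = −4.10 mmHg and the expected estimate is −4.63.

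**4. Primary facility test, no facility effect.** Let r be the same-eye IOP–facility correlation, and assume the cross-eye cross-parameter correlation is 0.4r. The bias is 0.06 × |r| × 0.6 × λ.

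| r | Bias, 80% responders (µL/min/mmHg) | One-sided error |
|---|---|---|
| 0 | 0 | 5% |
| −0.3 | 0.004 | 8% |
| −0.5 | 0.006 | 10% |
| −0.7 | 0.009 | 13% |

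- If the cross-eye cross-parameter correlation is 0 instead (SD 2.5), error is 10% and 16% at r = −0.3 and −0.5.
- With the Phase 1 mean fall of 4.6 mmHg (healthy volunteers, Protocol 1.2) and SD 2, bias is 0.002 to 0.005 and error 6.5% to 8.9% for r from −0.3 to −0.7.

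**The case against.** The best defence is that the primary test is barely touched. The documents give no IOP–facility correlation. In the Protocol 1.1 equation IOP also depends on EVP, inflow and uveoscleral outflow, and netarsudil is expected to act on EVP and inflow too. Even at r = −0.7 the bias is 0.009 against a planned 0.08. The 80% responder case is also the extreme, because the plan's 20% includes dropouts. If 10% are lost and 16 of the remaining 18 respond, the error is about 6.5% to 9.1% for the same r values and the IOP overstatement about 0.32 mmHg (SD 2.5). This stands: the damage to the primary test is modest and conditional.

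The largest IOP error rates need an ineffective drug. Prior studies make that unlikely, and an mITT of 3 to 5 subjects would show in the population counts of SAP 9. This also stands for that scenario. It does not answer the case where both eyes fall equally and 16 are kept, because the counts then look as planned.

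The within-netarsudil result is strictly forced only from about 12 subjects and only for the diurnal mean; the separate 13:00 and 16:00 tests are nearly rather than strictly forced. With no drug effect and small sets, rejection over all trials is roughly 63% to 91%. An estimate well beyond 2 mmHg would still say something about the drug. These limits are right, but at the planned 16 the diurnal test itself says nothing.

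Finally, the rule is prespecified and sized for, the IOP tests are secondary in a small Phase 2 study, and SAP 8.4 lists data for all randomised subjects. Prespecifying an outcome filter does not restore a test's level, and listings are not tests.

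**Conclusion.** The concern holds and should be corrected before analysis. Three conclusions need no assumed variance or correlation:

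- no planned efficacy test escapes the filter;
- the mean within-netarsudil diurnal IOP change must be −2 mmHg or lower whatever the drug does;
- at the planned 16 subjects its test must reject.

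The between-eye IOP bias favours netarsudil for any between-eye correlation below 1 with equal SDs. Its size rests on the assumed SD and correlation: 0.42 to 0.63 mmHg at 80% responders, and rejection of about 19% instead of 5% if both eyes fall equally. For the primary endpoint the bias is zero if IOP and facility changes are uncorrelated, and it raises the error to about 8% to 13% at correlations of −0.3 to −0.7 in the 80% case. Whatever the bias, the primary estimate describes responders and not the population named in the objective.

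**What to change.** Delete criterion 3 from the primary efficacy population in the Protocol synopsis, Protocol 9.3.1 and SAP 7.1. The population then consists of all randomised, dosed subjects with the 13:00 and 16:00 facility measurements at baseline and Day 8 that SAP 13.1 needs, with per-protocol a subset of that. Leave the as-treated rule unchanged. Keep the 2 mmHg responder set as a labelled supportive analysis.

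Restate the 20% allowance (Protocol synopsis, Protocol 9.2, SAP 5) without non-responders, and reconcile it with the 10% for non-completion or disqualification in Protocol 6.10. The two need not conflict today, since only the 20% counts IOP non-responders, but they should agree once non-responders are analysed.

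The cost is wording, with no extra subjects. The observed facility effect may be smaller. If 20% of subjects had no facility effect (an assumption), the mean is 0.8 × 0.08 = 0.064 and the SD is √(0.07² + 0.2 × 0.8 × 0.08²) = 0.077. Power is then 97% at n = 20, 96% at 18, 94.9% at 17 and 94% at 16. More than 95% therefore holds with the 18 subjects that a 10% loss leaves, but not with 16.
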